## **4.2. Rationale for Important Issues in the Study Design**

### **4.2.1. Choice of NTZ Dose and Duration of Treatment**

The dose of NTZ used for this clinical trial (600 mg b.i.d. for 5 days) has been associated with reductions in durations of illness in subjects infected with influenza, *Enterovirus/Rhinovirus*, and coronavirus. Dose-range-finding study RM08-3001 in subjects with influenza infection demonstrated a dose-dependent efficacy response with a 300 mg b.i.d. group demonstrating a non-significant improvement over placebo.

In clinical trials involving 2,659 subjects, adverse events reported by subjects receiving 600 mg NTZ b.i.d. for 5 days were similar to those of subjects receiving the placebo, with the exception of a higher rate of chromaturia (10.8% compared to 0.8% for the placebo). Studies of NTZ at higher doses have shown dose-dependent increases in the frequency of reported diarrhea and other gastrointestinal side effects, therefore no higher dose is planned for this study.

SARS-CoV-2 virus titer is believed to peak between the onset of symptoms and symptomatic day 4 and is not able to be cultured after seven days of symptoms ([Wölfel et al. 2020](#)). Antiviral treatment will have a reduced magnitude of treatment benefit when the host immune response is effectively decreasing the infectious viral load. Further, a study of remdesivir comparing 5- and 10-day courses of treatment found no difference between the two in patients with severe COVID-19 ([Goldman et al. 2020](#)). Therefore, it is unlikely that a course of treatment beyond five days will confer any significant additional benefit.

### **4.2.2. Choice of Duration of Follow Up**

A 28-day (+3 days) study duration is proposed, including five days on treatment and approximately 23 days of safety and symptom follow-up. As previously described, SARS-CoV-2 virus titer is believed to peak between the onset of symptoms and symptomatic day 4 and is not able to be cultured after seven days of symptoms ([Wölfel et al. 2020](#)). Further, onset of Acute Respiratory Distress Syndrome (ARDS) in patients infected with SARS-CoV-2 is approximately 8-12 days ([Li and Ma 2020](#)). Therefore, 28 days is expected to be a sufficient period of time to capture resolution of viral shedding and any hospitalizations or severe complications of illness. Any adverse events ongoing at the time of the Day 28 visit will be followed to resolution.

### **4.2.3. Choice of Control Group**

A placebo control is appropriate for the study due to lack of any approved active control.

### **4.2.4. Choice of Patient Population**

The population to be studied includes adults and adolescents with mild or moderate illness consistent with SARS-CoV-2 infection. Because there are no approved antivirals for the treatment

of mild or moderate COVID-19 in outpatients, subjects will not be prevented from being prescribed rescue medication for complications if warranted. Therefore, participation in the study will not pose unreasonable risk to any eligible subject. Discussion of specific eligibility criteria is presented below.

#### **4.2.4.1. Choice of Signs and Symptoms Required for Inclusion**

Data from studies RM08-3004 and RM08-3005 indicate that, in subjects infected with influenza, *EV/RV* or seasonal coronavirus, subjects with low symptom scores for the head, throat, nose, chest and cough symptom domains in the absence of elevated pulse or respiratory rate, illness may be expected to resolve quickly. These subjects have less opportunity to benefit from antiviral treatment. Further, subjects who indicate that symptoms are already improving are also unlikely to benefit from treatment. Therefore, subjects will be required to have a score of  $\geq 2$  for two respiratory symptom domains (head, throat, nose, chest, or cough) or a score of  $\geq 2$  for one respiratory symptom domain in the presence of elevated vital signs (pulse  $\geq 90$  beats per minute or respiratory rate  $\geq 16$  breaths per minute). Subjects will be excluded if they report having no symptoms (global assessment), being at their usual health, that their symptoms do not interfere with their usual activities, or that their symptoms have improved since yesterday. Subjects presenting with signs or symptoms consistent with severe COVID-19 (resting shortness of breath, resting pulse  $\geq 125$ , resting respiratory rate  $\geq 30$ ) will also be excluded from the study.

#### **4.2.4.2. Inclusion of Subjects At Least 12 Years of Age (No Upper Age Limit)**

The population to be studied includes adults and adolescents at least 12 years of age with mild or moderate COVID-19. This is a population similar to those selected for studies RM08-3001, RM08-3002, RM08-3003, RM08-3004 and RM08-3005 of the NTZ 300 mg extended release tablets in more than 5,000 subjects with colds or influenza-like illness. No safety concerns have been identified from these clinical trials. Data from pharmacokinetics studies in healthy volunteers 12 to 17 years of age or 18 to 65 years of age indicate that the pharmacokinetics of the major NTZ metabolites, tizoxanide and tizoxanide glucuronide, following oral administration of a NTZ 500 mg tablet are similar for these age groups. Safety data is also similar for these age groups. Therefore, the adult dose is deemed appropriate for pediatric patients down to 12 years of age. Informed consent will be required for subject participation in this study (see [Section 8.1.1](#)). A signed assent form will be required for any minors enrolled ( $\leq 18$  years of age or as local regulations apply) as well as signed parental/legal guardian consent by their parent/legal guardian allowing for the minor's participation.

#### **4.2.4.3. Inclusion of Subjects with Underlying Conditions**

For the present study, some subjects (e.g., subjects  $>65$  years of age, underlying asthma or COPD, diabetes mellitus, underlying cardiovascular disease, etc. – see [Inclusion/Exclusion criteria](#)) who are at higher risk of complications or exacerbations of underlying conditions will be allowed to participate if, in the judgment of the investigator, they are able to comply with protocol requirements and are not expected to require hospitalization. There is no approved antiviral for mild or moderate COVID-19, and subjects will not be prevented from being prescribed rescue medication for complications. Therefore, participation in the study will not pose unreasonable risk to any eligible subject.

The pharmacokinetics of the proposed dose of NTZ have been studied in subjects with renal and hepatic impairment and no dose adjustment is recommended in these populations. A thorough QTc study of NTZ at doses of 675 mg and 2700 mg found no prolongation of the QTc interval.

CYP450 inhibition assays indicate that tizoxanide inhibits CYP2C8 with an IC50 of 4.3 $\mu$ M, but a mechanistic static model used for potential drug-drug interactions indicated that a clinical interaction stemming from CYP2C8 inhibition by tizoxanide is unlikely.

While tizoxanide is more than 99.9% bound to plasma proteins, an *in vivo* drug-drug interaction study found no interaction between NTZ and warfarin. Tizoxanide inhibits the BCRP transporter and therefore may affect the pharmacokinetics of BCRP substrates, such as rosuvastatin. Co-administration of NTZ and rosuvastatin for seven days led to a 40% increase in the Cmax of rosuvastatin and 80% and 70% increases of rosuvastatin AUC0-t and AUC0- $\infty$ , respectively. However, the short duration of treatment in this study is not anticipated to cause adverse effects related to co-administration of NTZ and rosuvastatin.

For more detailed information, refer to the NT-300 Investigator's Brochure-COVID/VRI.

#### **4.2.4.4. Exclusion of Subjects with Significant Immunodeficiency**

Individuals with significant immunodeficiency, such as patients undergoing chemotherapy, transplant recipients receiving immunosuppressive therapy, and HIV patients with very low CD4 counts are more susceptible to longer durations of illness and more likely to experience complications due to viral respiratory infections. This is an important population in which to study antiviral drugs for the treatment of viral respiratory infections. Nonetheless, these subjects will be excluded from the present study due to (1) the likelihood of longer viral shedding necessitating longer courses or higher doses of treatment than what is proposed in this study, and (2) the likelihood that symptoms of illness may present differently in immunocompromised persons compared to immunocompetent persons due to reduced ability to produce the immune response that results in symptoms ([van der Vries et al. 2013, St. Jude Children's Research Hospital](#)).

#### **4.2.5. Use of Vitamin B Complex Supplement**

All subjects will receive a vitamin B complex supplement (Super B-ComplexTM, Igennus Healthcare Nutrition, Cambridge, UK) one tablet twice a day with study medication. This dose follows the manufacturer's labeled dosing. The purpose of the supplement is to help mask any chromaturia attributed to NTZ and aid in maintaining study blinding. The supplement will supply each subject with the following Percent Daily Values based on a 2,000 calorie diet: vitamin B1 1,333%, vitamin B2 824%, vitamin B3 240%, vitamin B5 360%, vitamin B6 1000%, vitamin B7 100%, vitamin B12 15,000%, folate 100%, and vitamin C 267%. Considering this supplement will provide well beyond the needed daily allowance of these water-soluble vitamins, excess amounts are expected to be excreted in the urine and provide discoloration.

#### **4.2.6. Choice of Patient-Reported Outcome Instrument**

This clinical trial will use the InFLUenza Patient-Reported Outcome Questionnaire (FLU-PRO©). FLU-PRO© was developed with the support of the U.S. Department of Health and Human Services through the National Cancer Institute and the National Institutes of Allergy and Infectious Diseases, National Institutes of Health, in response to the need for improved metrics to evaluate

treatment effect in clinical trials of drugs for the treatment of influenza and other respiratory tract viral diseases. It was developed and validated in accordance with FDA's guidance, "Patient-Reported Outcome Measures: Use in Medical Product Development to Support Labeling Claims." It has also been validated for use on an electronic device as part of an electronic diary ("eDiary") that can time stamp diary entries to ensure timely recording, thereby mitigating risks of recall bias. We will use an electronic diary for this clinical trial. FLU-PRO© was separately validated for use in a population with non-influenza like illness and also has recently been used in vaccine studies with older adults for the prevention of RSV (Powers et al. 2018, Yu et al. 2020). Data from Romark studies RM08-3004 and RM08-3005 also indicates validity and ability to detect change in patients infected with *Enterovirus/Rhinovirus* or seasonal coronavirus.

#### 4.2.7. Choice of Primary Endpoint

The primary endpoint was developed using data collected from 1,467 subjects infected with influenza, *Enterovirus/Rhinovirus* or seasonal coronaviruses during Romark studies RM08-3004 and RM08-3005. The endpoint defines a level of symptom improvement that constitutes a meaningful within-patient change in health status. The determination of meaningfulness was based on empiric evidence derived from the use of anchor questions. The endpoint requires (1) oral temperature <100.4 °F, (2) reduction of total symptom severity score from the previous day, (3) the patient to provide confirmation that symptoms are at least somewhat better, and (4) no symptom domain increase except below background levels for the remainder of the study (sustained response). These background levels were derived based on symptom scores reported by patients at the time they also reported being at usual health.

### 5. STUDY POPULATION

#### 5.1. Inclusion Criteria

1. Male or female outpatients at least 12 years of age
2. [Criterion removed in protocol amendment 2. See [Appendix 1](#) for revision history.]
3. Presence of clinical signs and/or symptoms consistent with worsening or stable mild or moderate COVID-19 (one of the following is required):
  - a. Presence of at least two respiratory symptom domains (head, throat, nose, chest, cough) with a score of  $\geq 2$  as determined by Screening FLU-PRO OR
  - b. Presence of at least one respiratory symptom domain (head, throat, nose, chest, cough) with a score of  $\geq 2$  as determined by Screening FLU-PRO with pulse rate  $\geq 90$  OR
  - c. Presence of at least one respiratory symptom domain (head, throat, nose, chest, cough) with a score of  $\geq 2$  as determined by Screening FLU-PRO with respiratory rate  $\geq 16$

AND patient reported assessment that symptoms are present, the symptoms are not consistent with the subject's usual health, the symptoms interfere with daily activities, and the symptoms have worsened or remained the same relative to the previous day, as confirmed by responses to questions in the Screening FLU-PRO.

4. Onset of symptoms no more than 72 hours before enrollment in the trial. Onset of symptoms is defined as the earlier of the first time at which the subject experienced subjective fever or any respiratory symptom (head, throat, nose, chest, or cough symptoms).
5. Willing and able to provide written informed consent (including assent by legal guardian if under 18 years of age) and comply with the requirements of the protocol, including completion of the subject diary and all protocol procedures.

## 5.2. Exclusion Criteria

1. Persons with any clinical sign or symptoms suggestive of severe systemic illness with COVID-19, including the following:
  - a. shortness of breath at rest,
  - b. resting pulse  $\geq 125$  beats per minute,
  - c. resting respiratory rate  $\geq 30$  breaths per minute, or
  - d.  $\text{SpO}_2 \leq 93\%$  on room air at sea level.
2. Subjects who experienced a previous episode of acute upper respiratory tract infection, otitis, bronchitis or sinusitis or received antibiotics for these conditions within two weeks prior to and including study day 1.
3. Severely immunodeficient persons including:
  - a. Subjects with immunologic disorders or receiving immunosuppressive therapy (e.g., for organ or bone marrow transplants, immunomodulatory therapies for certain autoimmune diseases)
  - b. Subjects with untreated HIV infection or treated HIV infection with a CD4 count below 350 cells/mm^3 in the last six months
  - c. Subjects actively undergoing systemic chemotherapy or radiotherapy treatment for malignancy
  - d. Subjects using steroids as maintenance therapy for chronic conditions
4. Subjects with active respiratory allergies or subjects expected to require anti-allergy medications during the study period for respiratory allergies.
5. Females of childbearing potential who are either pregnant or sexually active without the use of birth control. Female subjects of child-bearing potential that are sexually active must have a negative baseline pregnancy test and must agree to continue an acceptable method of birth control for the duration of the study and for 1 month post-treatment. A double barrier method, oral birth control pills administered for at least 2 monthly cycles prior to study drug administration, an IUD, or medroxyprogesterone acetate administered intramuscularly for a minimum of one month prior to study drug administration are acceptable methods of birth control for inclusion into the study. Female subjects are considered of childbearing potential unless they are postmenopausal (absence of menstrual bleeding for 1 year - or 6 months if laboratory confirmation of hormonal status), or have had a hysterectomy, bilateral tubal ligation or bilateral oophorectomy.
6. Subjects with a history of COVID-19 or known to have developed anti-SARS-CoV-2 antibodies.
7. Subjects residing in the same household with another subject participating in the study.

8. Treatment with any investigational drug or vaccine therapy within 30 days prior to screening and willing to avoid them during the course of the study.
9. Receipt of any dose of NTZ within seven days prior to screening.
10. Known sensitivity to NTZ or any of the excipients comprising the study medication.
11. Subjects unable to swallow oral tablets or capsules.
12. Subjects with known severe heart, lung, neurological or other systemic disease that the Investigator believes could preclude safe participation.
13. Subjects likely or expected to require hospitalization unrelated to COVID-19 during the study period.
14. Subjects taking medications considered to be major CYP2C8 substrates. Refer to [Table 5](#) in Section [6.5](#).
15. Subjects who, in the judgment of the Investigator, will be unlikely to comply with the requirements of this protocol including completion of the subject diary.

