## 2. INTRODUCTION

### 2.1. Coronavirus Disease 2019 (COVID-19)

Severe acute respiratory syndrome coronavirus 2 (SARS-CoV-2), a novel *betacoronavirus*, was isolated in December 2019 from patients presenting with unidentified viral pneumonia ([Zhu et al. 2020](#)). As of early June 2020, the virus resulted in more than 7 million infections and nearly 500,000 deaths worldwide ([Johns Hopkins Coronavirus Resource Center 2020](#)).

Infection with SARS-CoV-2 produces illness known as Coronavirus Disease 2019 or “COVID-19”. Commonly reported symptoms include fever, chills, cough, shortness of breath, difficulty breathing, fatigue, muscle or body aches, headache, new loss of taste or smell, sore throat, congestion or runny nose, nausea, vomiting, and diarrhea ([U.S. CDC 2020a](#)). The severity of illness ranges from mild and self-limited to very severe or fatal, with the current U.S. hospitalization rate of 82 per 100,000 cases and 255 per 100,000 in those over 65 years of age ([U.S. CDC 2020b](#)).

Seroprevalence studies conducted in U.S. metropolitan areas have estimated between 5% and 14% population-level exposure to SARS-CoV-2, indicating that a significant proportion of the population is still at risk for a first infection ([Sood et al. 2020](#), [Goldberg 2020](#)). Continued social distancing and “safer at home” measures aimed at reducing transmission of the virus has resulted in record unemployment in the U.S., and the SARS-CoV-2 pandemic is expected to result in a more than 10% reduction in U.S. domestic GDP in 2020 ([OECD 2020](#)).

Remdesivir for intravenous administration has received emergency use authorization in the U.S. for hospitalized patients with COVID-19, but no antiviral has been authorized or approved for mild or moderate illness.

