## 6.5. Concomitant Therapy

The following medications will not be allowed during the study: topical or systemic decongestants, nasal corticosteroids, and any prescription or non-prescription medications classified as (i) expectorants and cough preparations, (ii) analgesics and antipyretics, (iii) antihistamines (American Hospital Formulary Service (AHFS) classification) or (iv) medications considered major CYP2C8 substrates (see [Table 5](#) below). As an exception to this rule, subjects will be allowed to use acetaminophen and/or dextromethorphan as necessary for disabling symptoms.

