**Table 5: Major CYP2C8 Substrates**

Generic Name	Brand Name(s)	Therapeutic Use and/or Drug Class
Amodiaquine	BASOQUIN, CAMOQUIN, FLAVOQUIN	Antimalarial
Daprodustat (GSK1278863)	*	Antianemic, prolyl hydroxylase inhibitor
Dasabuvir (ABT-333)	EXVIERA	Antiviral, NSB5 inhibitor
Enzalutamide	XTANDI	Anticancer, antiandrogen
Montelukast	SINGULAIR	Antiasthmatic, LTRA
Pioglitazone	ACTOS	Antidiabetic, PPAR- $\gamma$ agonist
Repaglinide	NOVONORM, PRANDIN	Antidiabetic, meglitinide analog

Source: Backman et al. 2016

\*Currently listed as investigational only and not yet granted a trade name by the manufacturer

Subjects are also prohibited from taking hydroxychloroquine, chloroquine, remdesivir, azithromycin or lopinavir/ritonavir during the study except as standard-of-care rescue medication.

Medications for pre-existing conditions that are not excluded (see exclusion criteria) should be continued as prescribed. Standard-of-care rescue medication is permitted for complications of COVID-19 illness. The use of such medication will be recorded in the EDC system.

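### Exclusion criterion 8 states its willingness condition in the wrong direction, and no other rule covers investigational drugs or vaccines as a class

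*Protocol*

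**What the plan says.** Protocol Section 5.2, criterion 8, lists as a ground for exclusion: "Treatment with any investigational drug or vaccine therapy within 30 days prior to screening and willing to avoid them during the course of the study". The Synopsis (Section 1.1) carries the same sentence, so neither place corrects the other. The revision history in Appendix 1 records no change to it in any of the three amendments.

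The other rules that bear on outside treatment are these:

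- **Section 6.5, classes.** The list opens "The following medications will not be allowed during the study: topical or systemic decongestants, nasal corticosteroids" and continues with cough and cold preparations, analgesics and antipyretics, antihistamines, and major CYP2C8 substrates. Acetaminophen and dextromethorphan are excepted.
- **Section 6.5, named agents.** "Subjects are also prohibited from taking hydroxychloroquine, chloroquine, remdesivir, azithromycin or lopinavir/ritonavir during the study except as standard-of-care rescue medication".
- **Section 6.5, Table 5.** One of the barred CYP2C8 substrates, daprodustat, carries the footnote "Currently listed as investigational only and not yet granted a trade name by the manufacturer".
- **Section 5.1, criterion 5.** Subjects must be willing and able to "comply with the requirements of the protocol, including completion of the subject diary and all protocol procedures".

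Section 7 of the protocol and the SAP contain no rule on investigational drugs or vaccines.

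**The concern.** An exclusion criterion describes who is kept out. Here, being *willing* to stay away from other experimental agents is written as part of the reason for keeping a person out. Being *unwilling* never excludes anyone.

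Other experimental treatment is a foreseeable exposure in this setting. Section 2.1 says that "no antiviral has been authorized or approved for mild or moderate illness", and Section 4.2.2 sets the follow-up: "A 28-day (+3 days) study duration is proposed". An outside agent could act on the symptom diary behind the primary endpoint, on viral RNA, on the Day 22 antibody result, on progression to severe illness, or on the attribution of adverse events. The sponsor has already acted on related risks: Amendment 1 added the five named agents or combinations and the CYP2C8 rule. Criterion 8 was left as it stood.

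A second ambiguity lies in the same phrase. It is not certain that *investigational* also governs *vaccine*, so sites could differ over a subject who had a routine vaccination in the preceding 30 days.

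**Working it through.** There is no stated figure to reproduce. The check is a truth table, followed by a search for any other rule that would fill the gap.

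**Step 1: the rule as written.** Let R = treated with such an agent within 30 days before screening, and W = willing to avoid such agents during the study.

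- As written: excluded = R and W.
- Evident intent (inferred; the protocol does not state it separately): excluded = R or not W.

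| Recent use (R) | Willing (W) | As written | Evident intent |
|---|---|---|---|
| yes | yes | excluded | excluded |
| yes | no | eligible | excluded |
| no | yes | eligible | eligible |
| no | no | eligible | excluded |

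The written rule excludes 1 of 4 combinations and the evident intent excludes 3 of 4. The difference is 3 − 1 = 2 combinations, both with an unwilling subject. No combination is excluded that the intended rule would admit, so the written rule is too narrow and never too wide.

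If the intent were only the washout (excluded = R), 2 of 4 combinations should be excluded. The written rule would then still miss 2 − 1 = 1, the recent user who is unwilling.

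**Step 2: does another rule cover the missed combinations?**

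| Place | What it covers | Investigational drugs or vaccines as a class? |
|---|---|---|
| Section 5.1, criterion 5 | compliance with the protocol's requirements | no; it adds no ban of its own |
| Section 5.2, criterion 15 | subjects unlikely to comply | no; same reason |
| Section 6.5, text | symptom medicines, CYP2C8 substrates, five named agents or combinations (except as rescue) | no; nothing on vaccines |
| Section 6.5, Table 5 | seven substrates, one marked investigational | no; one drug only |
| Section 7 | reasons for stopping treatment | no |
| SAP | populations and analyses | no |

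There is partial cover for specific agents and none for the class.

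**Step 3: the consequence for the analysis.** SAP Section 2.2.1 defines the Per Protocol population as infected subjects without major deviations that may affect data integrity or the evaluation of effectiveness. Protocol Section 10.1.7 grades a deviation by its impact. Both presuppose a rule from which the subject departed. For an investigational agent not named in Section 6.5, the only candidate is the closing clause of criterion 8, which is an eligibility statement pointing the wrong way. Whether such use is a deviation is therefore open to argument.

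**The case against.** The strongest reply is that this is a slip whose meaning is obvious. A site would probably read criterion 8 as intended, and nothing shows that anyone applied it literally. That is fair, and it limits the weight of the point. It does not make the sentence correct, because eligibility should not depend on reading past the text.

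Three stronger readings are tempting and are not supported:

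- *That criterion 8 is the only protection against outside experimental treatment.* It is not. Section 6.5 bars five named agents or combinations except as rescue, and it bars daprodustat. Exclusions 3a and 3d also remove subjects on immunosuppressive therapy or maintenance steroids.
- *That co-treated subjects would necessarily stay in the Per Protocol analysis.* The definition of a major deviation in Section 10.1.7 is broad, and the sponsor could class such use under it before database lock. Use would also be visible: concomitant medications are recorded at Baseline, at the Day 4, 10 and 22 visits and at unscheduled visits, and SAP Section 6.4 lists and summarises them.
- *That excluding a recent user who agrees to abstain is itself an error.* The intended rule excludes that subject too.

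It is also true that symptom onset within 72 hours, with exclusion of previous COVID-19, leaves little room for earlier experimental treatment of the same illness. Prophylaxis, vaccine studies and use during the trial remain possible. Nothing in the documents suggests that such use would differ between blinded arms.

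On the vaccine phrase, the natural reading carries *investigational* to both nouns. The ambiguity is minor, but it sits in the same sentence and can be settled with it.

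**Conclusion.** Criterion 8 is wrong as written, in both places. Taken literally, it leaves eligible two of the four combinations of recent use and willingness that the sponsor evidently meant to exclude, or one of four if only the washout was intended. No other provision bars investigational drugs or vaccines as a class, so the deviation status of on-study use of an unnamed agent is unclear.

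The conclusion rests on the literal text and on an inferred intent. The number of subjects affected cannot be derived from the documents. No sample size, power or test in the plan depends on the criterion. The primary analysis is of all treated subjects positive at Baseline, so a deviation ruling would not change its population; the analysis that depends on such a ruling is the Per Protocol sensitivity analysis.

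**What to change.** In Section 5.2 and in the Synopsis, state the willingness condition in the right direction: treatment with such an agent within 30 days before screening, *or* unwilling to avoid them during the study. In the same sentence, make clear whether the vaccine must be investigational or whether any vaccine counts.

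Then reconcile the criterion with Section 6.5, including the exception for standard-of-care rescue, so that the two agree on whether on-study use is a deviation. What is permitted as concomitant or rescue treatment is for the sponsor to decide and is not proposed here.

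The cost is a few lines of text and a note to sites, with no new procedure or data item. Version 4.0 is dated January 11, 2021, and enrolment was expected to end that month, so the eligibility wording may come too late for most subjects. Settling the deviation status is still useful, provided it is done before database lock, when SAP Section 2.2.1 requires Per Protocol exclusions to be decided.
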